## Key

ပ

- Concomitant medications are to be recorded in the source records and appropriately reported in the EDC at each visit. ಚ
  - Physical exams may be performed on day 1 of every cycle (28 day cycles)
- Weight, PS and vital signs (temperature, blood pressure, pulse & respiratory rate) should be collected at each scheduled visit for physical examination. (For times of physical examination refer to
- Hematology assessments include complete blood count with differential and platelet count. During maintenance, labs may be performed on day 1 of every cycle (28 day cycles). Labs should be drawn per study schedule; however, routine labs will that are be drawn as per institutional standard of care will also be collected upon sponsor's request to assess safety. (Local labs will be accepted, these labs must be sent to the central site) ij
  - Chemistry assessments include glucose, bicarbonate, protein, serum creatinine, creatinine clearance, sodium, potassium, calcium, blood urea nitrogen (BUN), albumin, total bilirubin, alkaline phosphatase, AST, ALT and LDH. Chemistry labs should be drawn during maintenance on day 1 of every cycle (28 day cycles). Labs should be drawn per study schedule; however, routine labs will that are be drawn as per institutional standard of care will also be collected upon sponsor's request to assess safety. (Local labs will be accepted, these labs must be sent to the central site) ö
    - Bone marrow should be drawn as per the institutional standard of care during maintenance
    - Adverse events are to be assessed at each visit and recorded in the source records and appropriately reported in the EDC. r Fig.
- Crenolanib will be administered continuously on days 1-28 during each cycle of maintenance. Patients and/or a caregiver will be trained for home administration of the study medication. For crenolanib training must include the use of the patient diary (Appendix II), study drug storage, management of missed doses, and emergency contact information.
- This visit is strongly recommended, all measures should be taken to ensure this visit occurs. An End of Treatment visit should be performed within 30 days post last dose of crenolanib (prior to initiation of new treatment regimen or HSCT). This visit will include physical exams, vitals, ECOG PS, weight, CBC and CMPs; concomitant medications and adverse events should also be assessed. This visit will also require a whole blood sample to be drawn for biomarker and genetic testing.
  - An End of Study assessment will be performed for all patients to record overall survival. (This assessment will occur upon the completion of the study) ..

# STUDY SCHEDULE FOR ARM 2 (CRENOLANIB AND AZACITIDINE);

	Screening a		Cy.	Cycle 1 (28 days)		Cyc (28 c	Cycle 2 (28 days)	Cycle 3-N (28 days)	Maintenance b (up to 365 days)	End of Treatment c	End of Study d
	Day -28 to Day -	Day 1	Day 8	Day 15	Day 22	Day 1	Day 15	Day 1 of Cycle 3-N	Day 1 of Cycle N (1 cycle is 28 days)	Within 30 days post last dose of crenolanib	
Informed Consent e	×										
Inclusion/Exclusion f	×										
Demographics g	×										
Relevant medical history h	X										
Evaluation of FLT3 and other mutational status	x										
Concomitant medications i	X	x	×	X	X	X	×	X	X	X	
Physical examination j	X	х	×	X	х	X	X	×	X	X	
Vitals, ECOG PS, Weight, Height k	x	х	x	X	х	Х	X	x	X	X	
Hematology 	Х	Х	X	Х	Х	X	Х	X	X	X	
Blood chemistries m	Х	х	x	Х	Х	X	Х	X	X	X	
Pregnancy test n	Х										
EKG	X										
Echocardiogram	x										
Blood for PK analysis °		Х									
Blood for biomarker and genetic testing $_{\mbox{\scriptsize p}}$	×									x	
Bone marrow aspirations q	×						ьx				
Adverse events r		Х	х	Х	Х	X	Х	X	X	X	
Survival Follow-up											Х

## Key

- Screening procedures are to be performed  $\leq$  28 days prior to enrollment with the exception of the following: Hematology labs are to be drawn  $\leq$  7 days prior to enrollment, pregnancy test if applicable is to be performed ≤ 3 days prior to enrollment, and chemistry panel (with LFTs) is to be drawn ≤ 3 days prior to enrollment 4
  - Crenolanib may be administered for maintenance therapy for up to 365 days. Cycles of crenolanib will be 28 days. Physical exams, vitals, ECOG PS, weight, CBC and CMPs will be performed on Day 1 every cycle. At each visit concomitant medications and adverse events should be assessed.
- This visit is strongly recommended, all measures should be taken to ensure this visit occurs. An End of Treatment visit should be performed within 30 days post last dose of crenolanib (prior to initiation of new treatment regimen or HSCT). This visit will include physical exams, vitals, ECOG PS, weight, CBC and CMPs; concomitant medications and adverse events should also be
- Written consent must be obtained prior to performing any protocol-specific procedure. Results of a test performed as part of routine clinical management are acceptable in lieu of a screening test if assessed. This visit will also require a whole blood sample to be drawn for biomarker and genetic testing.

  An End of Study assessment will be performed for all patients to record overall survival. (This assessment will occur upon the completion of the study) ė d
- All inclusion/exclusion criteria should be met and confirmed by the sponsor prior to enrollment. ri isi ir
  - Demographics should be assessed at screening and are defined as race, ethnicity, age, and gender.

performed within the specified time frame.

Relevant medical history should be recorded in the EDC at screening.

- Concomitant medications are to be recorded in the source records and appropriately reported in the EDC at screening and each subsequent visit.
- Complete physical examination should be performed at screening, Cycle 1 day 1, 8, 15 and 22, Cycle 2 day 1 and 15 and on Day 1 of Cycle 3-N. Physical examination should be performed Day 1 of every cycle during maintenance. Physical examination should be performed at End of Treatment visit.
  - Weight, PS and vital signs (temperature, blood pressure, pulse & respiratory rate) should be collected at each scheduled visit for physical examination. (For times of physical examination refer to

10. CRITERIA FOR RESPONSE

For AML, response criteria will be modified from the International Working Group for AML [28]. Responders are patients who obtain a CR, CRi, or PR, with or without cytogenetic response, hematologic improvements, and morphologic leukemia-free state. Briefly, criteria are as follows:

(1).	Complete Remission (CR)
	Peripheral blood counts:
	No circulating blasts
	Neutrophil count $\geq 1.0 \times 10^9 / L$
	Platelet count $\geq 100 \text{ x} 10^9 / \text{L}$
	Bone marrow aspirate and biopsy:
	≤5% blasts
	No Auer rods
	No extramedullary leukemia
(2).	Complete Remission with Incomplete Blood Count Recovery (CRi)
	Peripheral blood counts:
	No circulating blasts
	Neutrophil count $<1.0 \times 10^9/L$ , or
	Platelet count $<100 \text{ x} 10^9/\text{L}$
	Bone marrow aspirate and biopsy:
	≤ 5% blasts
	No Auer rods
	No extramedullary leukemia
(3).	Partial Remission (PR)
	50 % reduction in bone marrow blast and to >5% and <20%.
(4).	Morphologic Leukemia-Free State
	Bone marrow: ≤ 5% myeloblasts
(5).	Hematologic Improvement (HI)
Her	natologic response must be described by the number of positively affected cell lines.
	Erythroid response (E) (pretreatment Hgb <11 g/dL)
	Hgb increase by $\ge 1.5 \text{ g/dL}$
	Platelet response (P) (pretreatment platelets $<100 \text{ x} 10^9/\text{L}$ )
	Absolute increase of $\ge 30 \times 10^9 / L$ for patients starting with $> 20 \times 10^9 / L$ platelets
	Increase from $\leq 20 \times 10^9/L$ to $\geq 20 \times 10^9/L$ and by at least $100\%$
	Neutrophil response (N) (pretreatment ANC <1.0 x10  /L)
	At least 100% increase and an absolute increase $> 0.5 \times 10^9/L$
	Blast response (B)
	At least a 50% reduction in blast percentage in peripheral blood (if > 5%) or bone marrow
	For high-risk MDS, response will use the International Working Group criteria [29].

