## 2.4.2. Clinical studies of Crenolanib in Relapse/Refractory FLT3 Mutated Acute Myeloid Leukemia

[figure not shown]
Crenolanib has been studied in relapsed/refractory FLT3 mutant AML (NCT01522469, NCT01657682). As of July 30, 2014, a total of 51 AML patients have been treated with single-agent crenolanib. Among those, 28 patients received fixed dose of crenolanib (300 mg) given as 100 mg TID; the other 23 patients received crenolanib using a body surface area (BSA) dosing schedule at 200 mg/m²/d. Patients had received a median number of 3 prior therapies for AML (range 1-7) including prior transplant and TKI therapy.

Of the 51 AML patients (FLT3 ITD, or FLT3 D835, or FLT3 ITD/D835) treated with crenolanib, 49

patients were eligible for efficacy evaluation. Crenolanib has demonstrated clinical activity in this heavily treated population. Several patients showed peripheral blast clearance after crenolanib therapy (Figure 2.5). Twenty-seven (27) patients demonstrated response, including 1 complete remission (CR) with full count recovery, 8 CR with incomplete hematological recovery

(CRi), 7 partial remissions (PR) and 11 blast responses as defined by adaptive Cheson criteria [10]. Clinical benefit rate was 55 %. Five (11 %) of these heavily pre-treated patients were bridged to transplant. Of the 25 patients with FLT3-D835 AML, 14 patients achieved a clinical benefit (56 %): 6 CR/CRi (24%), 4 PR (16 %), and 4 blast response (16 %).

Figure 2.5 Peripheral blast clearance in FLT3 mutant AML patients treated with crenolanib

\* Patients entered trials without peripheral blasts, † patients were not evaluable at cut off

Toxicity data from 38 patients is available. Commonly observed side effects included nausea (76 %), vomiting (52 %), diarrhea (47%), and transaminase elevations (8-11%). Two patients went off study due to toxicities, one due to nausea vomiting and one due to fatigue. Dose reduction occurred in 2 patients due to nausea and another due to transaminitis, respectively.

As of yet, QT prolongation has not been reported in 51 patients with AML treated with crenolanib. Most patients had received concomitant medication including antifungal medicine throughout crenolanib therapy; nonetheless no QT prolongation has been observed when EKG has been performed.

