#### 4.2. Exclusion Criteria

- 1. Absence of FLT-3 activating mutations at time of study screening
- 2. < 5% blasts in blood or marrow at screening, except if measurable extramedullary AML is confirmed
- 3. Subjects with Acute promyelocytic leukemia (APL)
- 4. Known clinically active CNS leukemia
- 5. Clinically active or unstable graft-versus-host disease requiring treatment which precludes administration of chemotherapy as defined in this protocol
- 6. Therapy with curative intent for relapsed AML or high-risk MDS prior to the first dose of crenolanib as follows: within 14 days of study enrollment for classical cytotoxic agents and for 5x the half-life for FLT3 targeting TKI, hypomethylating agents or MEK inhibitors
- 7. Patient with pre-existing liver diseases (i.e. cirrhosis, chronic hepatitis B or C, nonalcoholic steatohepatitis, sclerosing cholangitis)
- 8. Patients with known HIV infection
- 9. "Currently active" second malignancy (other than non-melanoma skin cancer, carcinoma in situ of the cervix or prostatic intraepithelial neoplasia within 1 year). Subjects are not considered to have a "currently active" malignancy if they have completed therapy and are considered by their physician to be at less than 30% risk of relapse within 1 year
- 10. Subject with concurrent severe and/or uncontrolled medical conditions that in the opinion of the investigator may impair the participation in the study or the evaluation of safety and/or efficacy.
- 11. Subject with uncontrolled cardiac disease including congestive heart failure class III or IV by the NYHA, unstable angina (anginal symptoms at rest) or new onset angina (began within the last 3 months) or myocardial infarction within the past 6 months
- 12. Pregnant or breastfeeding women
- 13. Inability to give an informed consent

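### The 5% floor in the AML partial-remission definition scores a deeper marrow response as a failure and a shallower one as a success

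*Combined protocol and SAP*

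**What the plan says.** Section 10 lists the AML categories:

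- **CR and CRi.** Marrow blasts of 5% or less and, for both, "No circulating blasts", absence of Auer rods, and "No extramedullary leukemia". The two differ only in neutrophil and platelet recovery.
- **PR.** "50 % reduction in bone marrow blast and to >5% and <20" per cent. No condition on blood, Auer rods or extramedullary disease is listed.
- **Morphologic leukemia-free state (MLFS).** "Bone marrow: ≤ 5% myeloblasts", and nothing else.

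The same section says who counts: "Responders are patients who obtain a CR, CRi, or PR, with or without cytogenetic response, hematologic improvements, and morphologic leukemia-free state".

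The phase II primary endpoint is the response rate after one or two cycles. Section 12.1 counts CR, CRi, CRp and PR; Section 12.4 counts CR, CRi and PR. MLFS is in neither formula.

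Extramedullary disease does not bar entry. Section 4.1 allows it apart from active CNS disease. Section 4.2 excludes "< 5% blasts in blood or marrow at screening, except if measurable extramedullary AML is confirmed", so some patients may enter with low marrow blasts.

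**The concern.** A response endpoint should be ordered: with everything else equal, fewer marrow blasts should never score worse. Here the PR band begins just above the level where CR and CRi end, but CR and CRi carry three further conditions that PR does not. A patient who crosses below the band without meeting those conditions leaves PR and does not reach CRi. The only category left is MLFS, which the endpoint omits.

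Two uses of the data depend on this classification: the phase II response rate for each arm, and the response count compared with the futility boundaries in Table 12.2. Both would be lowered by patients whose marrow did better than that of patients counted as successes.

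**Working it through.** **Step 1. Reproduce the plan's own figure.** Inputs from Section 12.1: n = 32, p0 = 0.10, p1 = 0.25, two-sided significance level 10% (z = 1.645), chi-square test.

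- Standard error under p0: sqrt(0.10 × 0.90 / 32) = 0.0530.
- Standard error under p1: sqrt(0.25 × 0.75 / 32) = 0.0765.
- Power = Φ((0.15 − 1.645 × 0.0530) / 0.0765) = Φ(0.82) = 0.794.

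This matches the stated 79%. The prior and cut-off in Section 12.1 also reproduce every response boundary in Table 12.2.

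**Step 2. Score example patients by the text of Section 10.** The 50% reduction is read as at least 50%. The last column applies the definition proposed under the fix.

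| Marrow blasts | Residual disease | Category as written | Counted as written | Counted after fix |
|---|---|---|---|---|
| 60% to 19% | circulating blasts and extramedullary | PR | yes | yes |
| 60% to 6% | circulating blasts | PR | yes | yes |
| 60% to 5% | circulating blasts | MLFS | no | yes |
| 60% to 1% | circulating blasts | MLFS | no | yes |
| 60% to 3% | extramedullary | MLFS | no | yes |
| 60% to 3% | none | CR/CRi | yes | yes |
| 12% to 6% | circulating blasts and extramedullary | PR | yes | yes |
| 10% to 5% | circulating blasts | MLFS | no | yes |
| 4% to 2% | extramedullary, unchanged | MLFS | no | no |

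Rows 2 to 4 isolate the problem. Baseline and residual disease are the same; only the final marrow value changes, and the better values score worse.

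**Step 3. Bound the affected group.** An AML patient with marrow of 5% or less and none of the three residual findings is CR or CRi whatever the counts. The inversion therefore reaches only patients with marrow at 5% or less plus circulating blasts, Auer rods or extramedullary leukemia. High-risk MDS uses separate criteria and is outside this point.

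**Step 4. Size per patient.** The frequency is not in the documents. As an assumed range, none, one or two such patients in an arm lower the rate by 0, 1/32 = 3.1 or 2/32 = 6.25 points.

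- Chi-square test against 10%: 5/32 gives z = (0.15625 − 0.10) / 0.0530 = 1.06, p = 0.289; 6/32 gives z = 1.65, p = 0.099.
- Exact 95% interval, which is the planned report: 5/32 gives 5.3% to 32.8%; 6/32 gives 7.2% to 36.4%. Both include 10%.
- Table 12.2: at 12 patients 0 responses stops an arm and 1 does not; at 24 patients 2 stops and 3 does not.

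**The case against.** Several objections have force.

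- **The source may say more.** Section 10 presents its list as a short, modified form of a published standard, so PR may carry further conditions there. That cannot be checked from the documents. Because the list is modified, the source cannot be assumed to govern, and the protocol writes these conditions out for CR and CRi but not for PR.
- **MLFS may be meant to count.** The responder sentence names it. Under the listed definitions CR and CRi always have marrow at 5% or less and PR never does, so naming MLFS as an optional accompaniment adds nothing; an intent to include it is possible. Both endpoint formulas point the other way. On either reading the text needs to say how MLFS is scored.
- **The floor does useful work.** Removing it outright would let a patient admitted under the extramedullary exception score PR for a fall from 4% to 2% with the mass unchanged. This stands, and the fix below keeps that protection.

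A reader might also infer more than the text supports:

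- *That PR with circulating blasts or extramedullary disease is itself an error.* PR describes residual leukemia. Allowing these findings is lenient but contradicts nothing in the protocol.
- *That a PR patient whose marrow later clears loses responder status.* Responders are those who obtain a response, and the endpoint covers one or two cycles. No rule cancels a PR obtained in that window.
- *That the single-agent data size the problem.* Section 2.4.2 reports 1 CR, 8 CRi and "7 partial remissions (PR) and 11 blast responses", so PR is 7/(1 + 8 + 7) = 44% of those remissions. That shows how common PR was with crenolanib alone, not how often a patient falls into the gap.
- *That one patient decides the arm.* The step from 5 to 6 responses crosses the 10% level only in the chi-square test used for sample size. The planned exact interval includes 10% at both counts.

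**Conclusion.** The defect is real. Followed exactly, Section 10 gives an inverted result on the primary endpoint: marrow blasts reduced by at least half to 5% or less, with circulating blasts, Auer rods or extramedullary leukemia remaining, is a non-response, while the same residual disease with marrow above 5% and below 20% is a response.

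This rests on two readings: that the list in Section 10 is what sites will apply, and that MLFS is not counted, as both endpoint formulas indicate. The effect is 3.1 points per affected patient in an arm of 32. The direction is toward undercounting, the group is narrow, and its frequency is unknown. The 79% power calculation stands as stated. The severity is should-fix: the categories are out of order whatever the frequency, but nothing in the documents shows that an arm's conclusion would turn on it.

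**What to change.** In Section 10, for AML patients with baseline marrow blasts above 5%, define PR as: *at least a 50% reduction in marrow blasts to below 20%, not meeting CR or CRi*. Marrow that falls by at least half to 5% or less and fails CR/CRi then counts at least as PR, and the order is restored.

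Add one sentence that patients admitted with under 5% marrow blasts under the extramedullary exception do not become PR through a marrow change alone. State in Sections 10, 12.1 and 12.4 that MLFS outside this definition is not a response, if that is the intent.

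Whether PR should also require clear blood or no extramedullary disease is a separate choice for the investigators. It is not needed to remove the inversion.

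The cost is one edited definition and one derivation rule, made by amendment and applied alike to the response rate and the futility count. It should be settled before phase II responses are counted, with the six phase I patients carried into each arm scored by the same rule. The downside is that a few patients change category.

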11. ADVERSE EVENT REPORTING

Adverse event is any untoward medical occurrence that may present during treatment with a pharmaceutical product, but does not necessarily have a causal relationship with this treatment.

Adverse drug reaction is a response to a drug that is noxious and unintended, which occurs at doses normally used in man for prophylaxis, diagnosis, or therapy of disease or for the modification of physiologic function.

Assessing causal connections between agents and disease is fundamental to the understanding of adverse drug reactions. In general, a drug may be considered a contributory cause of an adverse event if, had the drug not been administered, 1) the event would not have happened at all, 2) the event would have occurred later than it actually did, or 3) the event would have been less severe.

The Investigator or physician designee is responsible for verifying and providing source documentation for all adverse events and assigning the attribution for each event for all subjects enrolled on the trial.

Adverse Events (AEs) will be evaluated according to the latest CTC version 4.03 and documented in medical record.

Captured AEs include:

- 1) Any new AE regardless of its grade or expectedness post study drug initiation
- 2) Worsening of any expected or unexpected AEs determined by the principal investigator as related to crenolanib

### 11.1. Disease Related Events

Exported exents during loukeming thereny area

Adverse Events (AEs) will be evaluated according to the latest CTCAE version 4.03 and documented in medical record. Principal investigator should review and provide documentation of all baseline comorbidities related to the preexisting conditions and/or current medications prior to initiation of cycle one. These events will not be considered as related to crenolanib treatment. If these events continue during the treatment phase they do not need to be captured in the case report form.

LA	ected events during leakenna therapy are.
	Myelosuppression related events (due to disease or leukemia therapy)
	Febrile or infection episodes not requiring management in the intensive care unit
	Epistaxis or bleeding except for catastrophic CNS or pulmonary hemorrhage
	Anemia, neutropenia, lymphopenia, thrombocytopenia, leukopenia
11. 1	1.1. Symptoms Associated with Anemia:  Fatigue
	Weakness
	Shortness of breath
	Electrolyte abnormalities (sodium, potassium, bicarbonate, CO2, magnesium)
	Chemistry abnormalities (LDH, phosphorus, calcium, BUN, protein, albumin, uric acid, alkaline
	phosphatase, glucose)

### 11.1.2. General Therapy Related Events:

Catheter related events
Renal failure related to tumor lysis syndrome or antibiotic/ antifungal therapy
Rash related to antibiotic use
Hospitalization for the management of any of the above expected events

Abnormal hematologic values will not be recorded on the case report form. For abnormal chemical values, the apogee or nadir (whichever is appropriate) will be reported per course on the case report form.

the e	vent to the Safety Pr	oject Managei	in ORER	M and to	AROG.						
	m1 1 m 1 a a 1/2	1 ~			_				•		

☐ The MDACC "Internal SAE Report Form for Prompt Reporting" will be used for reporting to ORERM and to AROG.

Serious adverse events will be captured from the time the patient signs consent until 30 days after the last dose of drug. Serious adverse events must be followed until clinical recovery is complete and laboratory tests have returned to baseline, progression of the event has stabilized, or there has been acceptable resolution of the event.

Additionally, any serious adverse event that occur after the 30 day time period that is related to the study treatment must be reported to IRB, ORERM, and to AROG. This may include the development of a secondary malignancy.

